6.1.3 STIMULATION LEVEL OPTIMIZATION AND TREATMENT

The user first verifies that the electrodes are correctly positioned by inspecting the positioning guide, and ensuring the same number appears between the heavy bars of the positioning guide (refer to Step 3 above). In the majority of patients, the catheter will not need to be repositioned after it is inserted for the first time. In some patients, it may also be possible to visualize the oral guide in the throat. If the Sleeve is no longer aligned so that the electrodes are in the correct position, the Sleeve tube clamp can be opened and the Sleeve position adjusted until the correct positioning number is visible

CONFIDENTIAL Page 39 of 71

between the heavy bars of the positioning guide. Treatment can be carried out after confirming the proper placement.

- 1. The treatment cable from the Base Station is attached to the Phagenyx® Catheter.
- 2. The Base Station power is turned on.
- 3. The study-specific patient identifier is entered upon first treatment, and is re-called for subsequent treatments.
- 4. The patient's Threshold Level (lowest detectable level of stimulation) is established via incremental current increase from 5mA to 50mA in 1 mA steps. This is repeated three times, and the average of the three readings is used to determine the treatment level of stimulation.
- 5. The patient's Tolerance Level (highest tolerated level of stimulation) is established via incremental current increase from the Threshold value in 5mA to a maximum of 50mA. This is repeated three times, and the average of the three readings is used to determine the treatment level of stimulation.
- 6. The Stimulation Level is automatically calculated. This level is tested for eight seconds to ensure patient tolerability, and adjusted as needed.
- 7. The Stimulation Level is initiated, and lasts for up to 10 minutes. The patient is monitored/supervised throughout.
- 8. Steps 1-7 are repeated once per day for two subsequent consecutive days approximately 24 hours apart, for a total of three treatments over three days.
- 9. See the Instructions for Use (Phagenyx Base Station IFU) in the study's eTMF.

6.1.4 DISPOSAL

The Phagenyx® Catheter will become electronically locked once the 3-treatment regimen has been completed to prevent over-treatment or use of the device across multiple patients. If the catheter is not being used for feeding, it is removed after completion of the 3 treatments by a qualified health care provider and should be disposed of in medical waste as per site-specific procedure.

6.2 DEVICE ACCOUNTABILITY, LABELING AND STORAGE

6.2.1 ACCOUNTABILITY

Investigators will maintain accurate records of the receipt and disposition of the investigational device on the Device Disposition Log supplied by Phagenesis. The Log will be used to record device receipt, uses, discards, or returns. Device disposition will be verified by the clinical monitor periodically throughout the study. The investigator shall return the Base Stations, unused devices, and the completed device disposition log at completion of the investigation to Phagenesis or their designee, as directed. The investigator's copy of the Device Disposition Log must document the devices used in study patients as well as the unused devices that are returned to Phagenesis. Use of the Phagenyx System is prohibited outside of this protocol in US centers. In Europe, although the Phagenyx System is CE marked, the devices supplied for the study will be documented on the Device Disposition Log, stored in a secure area away from general stock, and only used for study patients.

CONFIDENTIAL Page 40 of 71

6.2.2 LABELING

In the US, the Phagenyx® System (Base Station and Catheters) will be labeled as investigational. In Europe, the device is CE-marked and will not be labeled investigational. The sites outside of the US will be provided an additional Base Station to be used for patients randomized to sham treatment. The Base Stations will be identified in such a manner to maintain the blind.

6.2.3 STORAGE

All Phagenyx® System components are to be stored in an ambient temperature-controlled, dry secure location where only authorized study personnel can access the devices for study use.

The Phagenyx® Base Station requires an overnight connection to an electrical outlet for overnight charging once a month.

6.3 MEASURES TO MINIMIZE BIAS: RANDOMIZATION AND BLINDING

All efforts will be taken to maximize treatment assignment blinding of the patient, caregivers, and third-party outcome assessors of clinical endpoints. Sites will be instructed to assign one healthcare professional to each enrolled patient to administer Phagenyx® treatment; this HCP shall not be blinded to the assigned patient's treatment. The designation of this individual will be at the discretion of the site investigator and may be a study nurse, SLP, or staff physician. The individual selected to administer the Phagenyx® treatment may not be an SLP or qualified health care provider who is otherwise involved with care of the study patient. Moreover, rating scales that reflect oral diet progression (e.g., Functional Oral Intake Scale and Dysphagia Severity Rating Scale) will also be completed by an SLP that is blinded to randomization assignment. All persons involved in placement of the catheter, assessments, treatment and follow up will be at the discretion of the investigator based on skill set and site standards, and will be further trained by the sponsor with a competency review completed.

Randomization will use stratification based on site and baseline PAS. minimization may also be included to ensure group balance for study site and additional baseline covariates Administrative permission to access the randomization assignment in the electronic database will be limited to unblinded HCPs who will administer treatment and who will monitor study compliance.

Stimulation parameters for the active treatment sessions will be collected on the eCRF to enable monitoring of the performance of the investigational device as well as to ensure proper treatment administration. Stimulation data will be monitored by a sponsor representative or designee who is uninvolved with the data analysis. The eCRF in which stimulation parameters are recorded will have strict administrative permissions, so that only the individual monitoring the investigational device will be allowed access. This monitor will also be responsible for monitoring compliance with the assigned treatment arm.

CONFIDENTIAL Page 41 of 71

Patients will be masked to treatment and will not be told if they receive the active or Some patients randomized to active treatment will have some sham treatment. sensation associated with the pharyngeal stimulation; however, a few with higher sensory thresholds may not feel anything as demonstrated in prior studies. The patients randomized to the sham treatment will not receive any actual stimulation and thus should not have any sensory feeling associated with the sham treatment. The informed consent documentation will advise that the patient "may or may not" feel the pharyngeal stimulation, so that those patients receiving either the active PES treatment of the sham treatment will not necessarily expect to feel anything. All procedural steps will be carried out in a very similar manner for both groups of patients. The only difference in the administration of the two treatments is that no electrical stimulation will be administered during the sham treatment. The way the treatment is administered will not give the patient any idea as to their treatment as there are no light or sound indicators associated with the administration of PES. Moreover, the individual administering treatment will be facing the patient at all times during the delivery of electrical (or sham) stimulations, and the base station will be facing the treatment administrator. The shape of the base station will prevent the patient from seeing what is on the administrator's screen during treatment delivery. The active/sham treatments will also be administered in privacy so that no other study personnel or patient caregivers/family members can observe the treatment or treatment assignment.

For those patients randomized to the sham group, a different Base Station will be used that delivers no electrical current and does not have the ability to treat with PES. This Base Station will have only "demo" software loaded, so the unblinded healthcare professional administering the treatment will have a screen and the ability to adjust the settings, without any changes or current begin delivered.

An assessment of whether the patient remains blinded will be included at the 14-day (+/- 1 day) or discharge whichever is first, follow-up assessment. This will be done via a question to the patient asking them if they believe they received the active or sham treatment and their response will be documented on the eCRF.

Evaluation of the VFSS will be performed by an external core lab that is not part of a study site. VFSS records will be anonymized so that records are only identified by site number, patient number, and type of study (i.e., baseline or follow-up). Core lab personnel will be blinded to the treatment assignment as well as the actual treatment received.

Protection of the blind will be maintained for the interim analyses. Study documents, analysis reports, closed meeting minutes and recommendations made by the Data Monitoring Committee will be maintained in a separate location not accessible by the sponsor or sites.

Patient data monitoring will be performed in a consistent and dynamic manner so that there will be no need to disrupt the normal study conduct to provide data needed for an

CONFIDENTIAL Page 42 of 71

interim analysis. Sites will not be told the results of any interim analysis unless the study is to be terminated early for either futility or success.

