2.3.2 DEVICE DESCRIPTION

The Phagenesis Phagenyx® System is indicated for the treatment of post-stroke neurogenic oropharyngeal dysphagia. Phagenyx® is a two-part neurostimulation system. It is composed of a durable component, the Base Station, and the single-use sterile disposable Phagenyx® Catheter. The Base Station acts as the user interface and provides the means to generate, optimize and monitor the delivery of electrical stimulation. The Phagenyx® Catheter design is based on that of an NGT, but incorporates electrodes with appropriate wiring and insulation for delivery of electrical stimulation to the pharyngeal mucosa. The Phagenyx® Catheter has been designed to also deliver enteral nutrition to the patient as needed. Phagenyx® received CE Mark in 2012.

The Base Station has the following functions:

- Stimulation Generation, optimization and output of controlled electrical stimulation
- User Interface Receives, stores and outputs data regarding the patient, user, product and treatment

Figure 4 provides the front and back appearances of the Base Station with key features labeled.

CONFIDENTIAL Page 21 of 71

The design of the Base Station and associated software complies with medical device electrical and software standards. Moreover, appropriate hardware risk control measures have been taken so that a software failure is not associated with risk of serious injury. Hence, the overall safety of the Phagenyx® System is Class A.

Figure 4: Phagenyx® Base Station with labeled components:

- a) Touchscreen Touch sensitive glass screen
- b) Casework High density Acrylobutdiene Styrene (ABS.) Easy clean surface
- c) On/Off switch Push button switch with integrated LED indicator to show when unit is turned on
- d) USB port cover Easy lift material to provide protection and convenient access to USB port
- e) Current and battery indicators Lights to show when system is actively delivering current or being charged
- f) Connector to Phagenyx® Catheter For connection to the Smart Connector on the Phagenyx® Catheter prior to treatment
- g) Cable clip Securing point for the treatment cable
- h) Cable tidy Convenient storage position for the treatment cable
- i) Treatment cable Cable and connector through which data and the treatment current is delivered to the patient
- j) Cable groove Retaining feature on the cable tidy to ensure the correct tension is applied to the Treatment cable

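### Section 6.3 says no light is associated with PES, yet the device description lists a light showing current delivery; its behaviour on the sham unit and its visibility to the patient are not addressed

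*Protocol*

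**What the plan says.** Protocol section 6.3 argues that the way treatment is given will not reveal the arm to the patient. One reason given is that "there are no light or sound indicators associated with the administration of PES". Other reasons follow in the same section. On orientation, it states that "the base station will be facing the treatment administrator". It adds that the unit's shape keeps the screen out of the patient's view, and that sessions are "administered in privacy so that no other study personnel or patient caregivers/family members can observe the treatment or treatment assignment". The consent wording also leaves open whether the patient will feel anything.

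For the sham arm, section 6.3 says that "a different Base Station will be used that delivers no electrical current and does not have the ability to treat with PES". That unit runs demonstration software, described only as giving the administrator a screen and settings that can be adjusted without effect.

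Section 2.3.2 describes the Base Station part by part in the legend to Figure 4. Item e is "Current and battery indicators Lights to show when system is actively delivering current or being charged". It is listed separately from the touchscreen (item a) and from the power switch with its own LED (item c).

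Section 6.2.2, on labeling, adds that "The Base Stations will be identified in such a manner to maintain the blind".

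**The concern.** A light that comes on when current flows is a light indicator associated with giving PES, so the premise in section 6.3 conflicts with the protocol's own device description. The conflict matters because the two arms use different units and only one of them delivers current. If the light follows the current, it marks the active arm.

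The trial is presented as patient-masked and sham-controlled. A patient who can see an arm-specific signal on three consecutive days has a cue beyond sensation. Section 6.3 relies on sensation being ambiguous: some active patients may feel nothing, and all are told that they may or may not feel the stimulation. A visible light could remove that ambiguity even for active patients who feel nothing. Belief about the assigned arm could then colour what patients report about themselves.

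**Working it through.** No arithmetic applies. The check sets the relevant texts side by side.

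**Step 1: the two statements.** Section 6.3 makes an unqualified denial of any light or sound indicator associated with PES. Section 2.3.2, item e, makes an unqualified statement that lights show active current delivery. Section 6.3 may have meant only that the patient sees no such light, but it does not say so.

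**Step 2: the sham unit.** It is a different Base Station, delivers no current and runs demonstration software. I looked in both documents for any statement that this software lights the item e indicator, or that the light is covered, disabled or imitated. There is none.

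**Step 3: do the other safeguards cover the light?**

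| Safeguard | Where | What it covers |
|---|---|---|
| Station faces the administrator | Protocol 6.3 | The whole unit; the light's position is not stated |
| Shape of the station | Protocol 6.3 | The screen only |
| Privacy of sessions | Protocol 6.3 | Other staff and family, not the patient |
| Identification of Base Stations | Protocol 6.2.2 | A general aim; the light is not mentioned |
| Similar procedural steps in both arms | Protocol 6.3 | The procedure in general; the light is not mentioned |

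Orientation is the most relevant safeguard and may be enough in practice. The text does not say whether the light can be seen from the patient's side. Figure 4 is missing from the text copy used here and may settle its position; its absence is not counted against the plan.

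**Step 4: what must hold for the light to unmask a patient.** Two conditions are needed, and the documents establish neither.

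| | Sham unit lights the indicator identically | Sham unit does not |
|---|---|---|
| Patient cannot see the light | No cue | No cue |
| Patient can see the light | No arm difference | Light on in active sessions, off in sham sessions |

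Only one of the four cells gives a cue. In that cell it is present in all three of a patient's sessions; in the others, in none.

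**Step 5: which outcomes could be touched.**
- Primary endpoint: the PAS is read by an external core lab blinded to assignment (Protocol 6.3). Less of a concern.
- FOIS at 7 days: first secondary endpoint in the testing order (Protocol 9.4.3). A blinded speech-language pathologist completes it (6.3), but patient reports are among the permitted sources (8.1.7).
- Barthel Index: completed by the patient (8.1.4). Exploratory.
- EQ-5D with EQ-VAS: the VAS is the respondent's own rating (8.1.9). Exploratory.

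The patient is asked to guess the arm at 14 days or discharge (Protocol 6.3; SAP Table 1), but the SAP describes no analysis of the answers, so the planned analyses would not examine the effect of such a cue.

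**The case against.** The case on the other side is substantial.

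- **Masking does not depend on one sentence.** A reader might infer that the whole masking argument falls with the no-light statement. It does not: section 6.3 also relies on orientation, shape, privacy, the demonstration unit and the consent wording. Orientation in particular concerns the whole station. This stands.
- **The light may be a weak cue.** Each patient is assigned to one arm, has no second unit for comparison, and would need to know what the light means. Item e also groups current and battery indicators together. This lowers the weight of the point but does not remove it.
- **Sensation is probably the stronger cue.** Active patients go through threshold and tolerance testing, each repeated three times (Protocol 6.1.3), while sham patients should feel nothing (6.3). Dealing with the light leaves that untouched. True, but it is no reason to leave a second, avoidable cue in place.
- **The main outcomes are protected.** The core lab is blinded, FOIS and DSRS are completed by a blinded rater, and the patient-completed scales are exploratory. This stands, and it keeps the point modest.

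None of this reconciles sections 2.3.2 and 6.3, and no argument offered there deals with the light itself.

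**Conclusion.** The contradiction is certain on the text: one stated reason for expecting the patient blind to hold is wrong as worded. What follows from it is only possible. As described, the light could differ by arm, and it would be a cue only if the patient can see it and the demonstration unit does not light it in the same way.

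Two stronger readings are tempting. One is that the light separates active from sham in every session. That assumes both conditions of step 4, and the documents give neither. The other is that patient-reported outcomes are biased. The documents show a route by which they could be, but give nothing from which a size or even a direction could be derived. The concern is therefore confined to FOIS where it rests on patient report, the Barthel Index and EQ-5D/EQ-VAS, and it is smaller for the primary endpoint. It still merits correction before randomization, because the sponsor can settle both unknowns by inspecting the two units.

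**What to change.** 1. Reconcile sections 2.3.2 and 6.3. Replace the no-light sentence with a statement of what the current indicator does on the active and sham units, and how the patient is kept from learning the arm from it.
2. Either have the demonstration unit light the indicator exactly as the active unit does, or shield the light from the patient's side on all study Base Stations. Both leave the indicator working for the unblinded administrator, which is preferable to disabling it.
3. Verify this on both the active and the sham unit in site training before the site starts randomizing. Roll-in sessions alone are not enough: roll-in patients are unblinded and all receive active treatment, and European sites may have none (Protocol 4.1).

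The cost is a shield or a software setting, a short added check in training, and one corrected sentence. If inspection shows that the light already behaves identically, or cannot be seen from the patient's position, only the sentence needs to change.

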A core laboratory will be established for analysis of all procedural VFSS. The VFSS core lab will provide standardized baseline and follow-up analyses of the primary endpoint as well as VFSS-related tertiary endpoints. Personnel at the VFSS core lab will also be blinded to patient treatment assignment.

Up to three unblinded, active treatment roll-in patients will first be enrolled at each site in the US. The need for roll-in patients for European sites will be based on experience with the CE-marked device at the site and will be agreed to by Phagenesis and the site investigator. Roll-in patients will enable the site study staff to become fully proficient in the most effective way to administer the Phagenyx® treatment as well as perform other protocol-specific assessments. The sponsor will provide detailed training and education to the site staff in the use of the Phagenyx system and the protocol. The sponsor will provide an on-site representative to oversee and provide aid in the administration of PES during treatment of these roll-in patients. The sponsor will complete the Site Training and Competency Review form during the visit(s). The site will be approved to begin randomizing patients after the site meets the following competency requirements:

- The treatment administrator successfully and confidently completes up to three treatment sessions with little to no prompting or other aid from the sponsor representative,
- The treatment parameters recorded on the Base Station reflect appropriate stimulation levels, and
- Electronic case report forms (eCRFs) for baseline through the acute follow-up visit are completed correctly within 5 days of enrollment then within 5 days of each follow up for the roll-in patients.

CONFIDENTIAL Page 33 of 71

A formal review of site competency will be made after one to three roll-in patients have been treated, and the site is competent based on the above parameters. The site investigator and other relevant personnel will meet with sponsor personnel or their designee(s) via teleconference or on site to review the roll-in patient records and answer outstanding questions. The sponsor or their designee will provide approval to begin randomizing patients by controlling access to the randomization module of the study's EDC system. Meeting documentation including recommended actions and decisions will be retained in the eTMF for each site.

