10.2 CORE LABORATORY

A core laboratory will be established for VFSS analysis. Standardized protocols for acquiring, transmitting, and analyzing electronic records will be developed and documented prior to study initiation. Protocols for the transmission of electronic media files will strip personal identifiers from the media. The core laboratory will maintain copies of correspondence, data, and other records related to the clinical study as appropriate. Refer to the Core Lab Manual of Operations for specific information.

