4. STATISTICAL METHODS

4.1. Statistical Hypotheses

The primary efficacy analysis is based on an ordinal logistic model of PAS (1-8 scale) of each bolus, determined by VFSS 48 hours following the last investigational treatment, and converted to a trichotomized response as follows: Safe (PAS 1-3), Penetration (PAS 4-5), or Aspiration (PAS 6-8). Hypothesis testing will be a superiority test performed on the main effect of treatment, β_{trt} , i.e., the difference in cumulative log odds between treatment groups, with $\beta_{trt} > 0$ indicating the PES group has higher odds of a safer responses than the control group.

- Primary Efficacy Endpoint: The null hypothesis is that $\beta_{trt} \leq 0$ (PES does not result in safer swallows than the control treatment), and the alternative hypothesis is that $\beta_{trt} > 0$ (PES results in safer swallows than the control treatment).
- If the primary endpoint meets statistical significance then formal testing and analysis for the secondary endpoint will be carried out.

The analysis of the secondary endpoint of FIOS is based on a Cochran-Mantel-Haenszel (CMH), stratified by site and baseline PAS, using the modified ridit score and test of "row mean scores different" to take into account the ordered nature of the response.

The analysis of the secondary endpoint of DSRS is based on an ANCOVA model of mean DSRS 48 hours after the last study treatment, adjusting for baseline. Hypothesis testing will be a superiority test performed on the main effect of treatment, δ , with $\delta \ge 0$ indicating the PES group has lower mean DSRS than the control group.

• Secondary Efficacy Endpoint of DSRS: The null hypothesis for the $\delta \leq 0$ (PES does not result in lower DSRS), and the alternative hypothesis is that $\delta > 0$ (PES results in lower DSRS).

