4.8. Efficacy Evaluation

4.6.1 Primary Efficacy Analysis

The primary endpoint is trichotomized PAS on each bolus, determined by VFSS 48 hours (+/- 24 hours) after completion of PES treatment. The three ordinal PAS categories are defined as Safe (PAS 1-3), Penetration (PAS 4-5), and Aspiration (PAS 6-8). Each patient contributes 12 measurements to the primary endpoint, of which six are from boli of a thin consistency and 6 are from boli of a nectar consistency.

The ITT population will be used for the primary analysis.

A cumulative logistic model will be used to analyze the primary endpoint, and a sandwich variance estimator via a generalized estimating equations approach will be used to account for correlated PAS outcomes within each patient.

The statistical model for the primary analysis will include treatment, bolus consistency, baseline maximum PAS, and treatment by consistency interaction as predictors. The response of individual i on bolus t is coded as $y_{it} = 1$ for a safe swallow, $y_{it} = 2$ for a swallow resulting in penetration, and $y_{it} = 3$ for a swallow resulting in aspiration. The log odds of a swallow with response $\leq j$ conditional on predictors x_{it} is modeled as

$$logit(P(y_{it} \le j | x_{it}))$$

$$= \beta_j + \beta_{base} * base_{it} + \beta_{trt} * trt_i + \beta_{nectar} * nectar_t + \beta_{trt*nectar} trt_i * nectar_t$$

with ordered intercept terms $\beta_1 < \beta_2$, a treatment indicator trt_i (1=PES, 0=control), and a consistency indicator $nectar_i$ (1=nectar, 0=thin). The maximum PAS (1-8) of individual i across all pre-treatment swallows of a given consistency at baseline is denoted $base_{it}$. The GEE approach with robust sandwich estimator is used to account for within subject correlation.

Missing PAS data will be imputed in the primary analysis. PAS values that are missing due to application of VFSS stopping criteria will be assigned the worst (highest) post-treatment PAS value. For patients who have no post-treatment PAS data due to lost-to-follow-up or death, the post-treatment PAS values will be imputed from baseline PAS values and other patient baseline characteristics using multiple imputation. In addition, tipping point analysis will be performed as a sensitivity analysis.

The estimated treatment effect in the logistic model will be presented along with standard error. The treatment effect will also be presented as an odds ratio with 95% confidence interval.

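### The core lab's VFSS records carry patient number and time point, an avoidable reader-expectation risk that cannot create a false benefit but can modestly attenuate the primary odds ratio

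*Protocol*

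**What the plan says.** The core laboratory supplies the primary endpoint. Protocol 4.1 says: "The VFSS core lab will provide standardized baseline and follow-up analyses of the primary endpoint". Protocol 6.3 sets the labelling rule: "VFSS records will be anonymized so that records are only identified by site number, patient number, and type of study (i.e., baseline or follow-up"). Its next sentence covers treatment arm: "Core lab personnel will be blinded to the treatment assignment as well as the actual treatment received".

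On the outcome, SAP 4.6.1 says: "The primary endpoint is trichotomized PAS on each bolus, determined by VFSS 48 hours (+/- 24 hours) after completion of PES treatment". The tested effect, in SAP 4.1, is "the difference in cumulative log odds between treatment groups". Baseline enters the model only as a covariate, the highest PAS among a patient's pre-treatment swallows of the same consistency. Eligibility on baseline PAS is judged by site clinical staff, not by the core lab (Protocol 5.1).

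Neither document describes hiding the time point from readers or randomizing the reading order. Protocol 10.2 defers the procedure: "Refer to the Core Lab Manual of Operations for specific information". That manual is not among the documents.

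**The concern.** PAS scoring is a judgement about how far material enters the airway and how the patient responds, and the primary analysis cuts the scale between 3 and 4 and between 5 and 6. A reader who sees a baseline label knows that the site has already judged this patient's swallowing unsafe, because entry requires it. A reader who sees a follow-up label has reason to expect recovery. The patient number also lets the second reading be anchored on the first. Blinding to arm does not remove either influence.

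Three things could be affected:

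- **The primary odds ratio**, if expectation makes follow-up scoring less accurate.
- **The baseline covariate.** It is a maximum, so one borderline swallow read harshly can set it.
- **Within-patient readings across the two exams**, such as change in MBSImP, or a before-after summary of the roll-in patients if one is reported.

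**Working it through.** **Inputs from the documents.** Odds ratio 2.23 and 95% power for the primary endpoint (SAP 4.2); 180 evaluable patients, up to 270 after re-assessment, 20% dropout (SAP 4.2); one-sided 0.025 (SAP 4.3.1); final critical value 1.9929 (SAP 4.5.3). SAP 4.5.4 prints 2.5093 for the final test. That is a separate matter, and 1.9929 is used here.

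**Assumptions not in the documents.** 1:1 allocation, the sham category mix, the within-patient correlation, and the size and form of any lenient reading.

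**1. The plan's own figures.** 180/0.8 = 225 and 270/0.8 = 337.5, rounded up to 338; both agree. The Lan-DeMets O'Brien-Fleming boundaries at 2/3 information come out at 2.5093 and 1.9929; both agree. The 95% power was simulated and cannot be reproduced, because the sham mix, correlation and adaptation zones are not given. Treated as one fixed look, it implies a standard error of ln(2.23)/(1.9929 + 1.645) = 0.8020/3.638 = 0.220.

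**2. Uniform leniency.** If readers relax a threshold equally in both arms, the odds at cut j are multiplied by the same factor exp(s) in each arm, and the factor cancels from the ratio. Example: sham 40% safe gives odds 0.667, and PES odds are 0.667 × 2.23 = 1.487. A shift of 0.5 logits gives 1.099 and 2.451, and 2.451/1.099 = 2.23. Shifts of 0.25 to 1.0 logits all return 2.23.

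**3. Leniency as misclassification.** Let a random fraction f of unsafe follow-up swallows be read one category safer, in both arms. Take sham at 40% safe, 25% penetration, 35% aspiration, and f = 10%.

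- True PES mix at odds ratio 2.23: 59.8%, 20.8%, 19.4%.
- Sham as read: safe 40 + 2.5 = 42.5%; safe or penetration 65 + 3.5 = 68.5%.
- PES as read: safe 59.8 + 2.1 = 61.9%; safe or penetration 80.6 + 1.9 = 82.5%.
- Odds ratios at the two cuts are about 2.19 and 2.17. The common proportional-odds fit is 2.19.

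Approximate power is Φ(ln(OR)/0.220 − 1.9929). Four sham mixes (safe/aspiration 20/60, 30/45, 40/35 and 50/30%) give these ranges:

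| f | fitted odds ratio | approximate power |
|---|---|---|
| 0 | 2.23 | 95% |
| 5% | 2.17–2.22 | 93.5–94.7% |
| 10% | 2.12–2.20 | 92–94% |
| 20% | 2.04–2.18 | 89–94% |

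**4. Clustered simulation.** 12 correlated swallows per patient, 180 patients, sandwich standard errors, no interim looks and no covariates; 600 runs per setting.

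- With patient SD 3.0 on the logit scale (chosen because power is then near 95%), the mean odds ratio goes 2.35, 2.28, 2.19 and power 95.3%, 95.2%, 94.5% at f = 0, 10% and 20%. Read the change, not the level, since the start is 2.35 rather than 2.23.
- With SD 2.5, power goes 97.7%, 96.2%, 95.7%.
- Monte Carlo error is about √(0.95 × 0.05/600) = 0.9 points per figure, so these differences are barely resolved.
- Uniform shifts of 0.5 and 1.0 at SD 3.0 left the odds ratio at 2.34 and 2.36. Power was 94.2% and 92.8%, which is a loss of precision, not bias.

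**5. No true effect.** If the arms do not differ, the same misreading in each leaves them equal, so the odds ratio stays 1.00. Simulated rejection was 2.6% without misreading and 2.4% at f = 20% (4,000 runs each, SD 3.0). Runs of 1,500 at f = 20% gave 3.1–3.2%, with Monte Carlo error about 0.4 points and no matched run without misreading. The longer matched pair shows no inflation.

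**The case against.** The strongest reply is that the primary comparison is already protected. Every primary reading is a follow-up exam, in both arms, scored without knowledge of assigned or received treatment. Time point cannot differ by arm, so any expectation is shared. That stands, and it rules out a false-positive mechanism.

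Second, Protocol 6.3 describes how records are identified, not what a reader has on screen, and the unseen manual may specify shuffled or unpaired reading. This stands in part. It is not established that readers use the label or read in pairs. But the protocol makes a positive statement about labelling, and a manual that hid the time point would depart from it.

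Third, masking would be imperfect, because catheters kept for feeding stay in after treatment. True, but partial masking is still better than a printed label.

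Stronger readings that a reader might infer, and that the documents do not support:

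- **That the odds ratio must shrink.** Lenient reading of borderline swallows is naturally a threshold shift, which leaves it unchanged.
- **That the loss is larger**, from a calculation that sends a share of all unsafe swallows straight to safe. That includes clear aspiration and collapses a three-category endpoint to two.
- **That the MBSImP data have no sham comparison.** SAP 4.6.3 summarizes exploratory endpoints by treatment group.
- **That roll-in efficacy results are biased.** The documents say only that roll-in patients are analyzed separately and specify no before-after efficacy analysis.

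**Conclusion.** The point holds as a small, conservative risk. The label allows readers to know the time point and to link exams, and nothing in the two documents offsets this. It cannot create an apparent benefit. Attenuation arises only if expectation or anchoring acts as misclassification. At an assumed 10% one-category downgrading the odds ratio is about 2.12 to 2.20 instead of 2.23, and the power loss is under 1 point in the clustered simulation at SD 3.0 and up to about 3 points in the fixed-standard-error approximation. Power in that approximation stays above the 90% claimed in Protocol 9.2; only at 20% downgrading with the most severe sham mix does it reach 89%.

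The effect on the baseline covariate was not quantified. It is unrelated to arm, so the likely cost is noise. The effect on within-patient change is more direct, but those outputs are exploratory or not specified. All sizes rest on assumed misreading rates and sham mixes; the documents give neither.

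**What to change.** Amend the labelling sentence in Protocol 6.3, and the Core Lab Manual to match, so that:

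- each exam reaches readers under a random exam code, with no patient number and no time point;
- baseline and follow-up exams are read in shuffled order, in batches sized to have scores ready for the interim analyses at 60 and 120 patients;
- codes are linked to patients only after the scores in a batch are locked.

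If the sponsor believes readers need the time point, the protocol should say why. The cost is a coding and batching step. No extra reads are needed, and the sample size and analysis model do not change. A catheter still in place will unmask some follow-up exams.
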